9.11.2 Clinical Laboratory Evaluation

All laboratory tests will be presented in System International (S.I.) units only, unless otherwise specified.

Subject Samples:	Tables	Safety sample
	Listings	All subjects consented
	Figures	Not applicable
Subgroups:		Not applicable
Abbreviation:		LB

Standard Presentations

- LBT001 For those variables with a PCS criterion (as defined in [Table 4](#)) the incidence of marked abnormalities per laboratory parameter will be presented. The percentage per parameter is defined as the ratio of the number of subjects with at least one PCS value occurring at a post-baseline visit and the total number of subjects in the subject sample with a post-baseline measurement of the specified parameter.
- LBT002 Summary of quantitative special laboratory parameters for determination of vitamin deficiencies, for all centers/countries combined, using default summary statistics. At each assessed visit, summary statistics will be presented as well as for the change from Baseline at each post-baseline visit.
- LBT003 The incidence of values above and below the reference range for the quantitative special laboratory parameters for determination of vitamin deficiencies will be presented. The percentage per parameter is defined as the ratio of the number of subjects with at least one value above (below) the reference range at a post-baseline visit and the total number of subjects in the subject sample with a post-baseline measurement of the specified parameter.

The laboratory test data will be presented in subject data listings as follows:

- LBL001 Hematology laboratory test data will be presented by-subject and within-subject by sample collection date and laboratory test, including the relevant reference ranges.
- LBL002 Chemistry laboratory test data will be presented by-subject and within-subject by sample collection date and laboratory test, including the relevant reference ranges.
- LBL003 Urinalysis laboratory test data will be presented by-subject and within-subject by sample collection date and laboratory test, including the relevant reference ranges.
- LBL004 Laboratory test data will be presented by-subject and within-subject by laboratory test. PCS values will be identified and only subjects with one or more PCS values for the laboratory test will be presented.

9.11.3 Vital Signs

Subject Samples:	Tables	Safety sample
	Listings	All subjects consented
	Figures	Not applicable
Subgroups:		Not applicable
Abbreviation:		VS

Standard Presentations

- VST001 Summary of quantitative vital signs assessments will be presented, for all centers/countries combined, using default summary statistics. At each assessed visit, summary statistics will be presented as well as for the change from Baseline at each post-baseline visit.
- VST002 For each variable with a PCS criterion (as presented in [Table 5](#)), the incidence of PCS values will be presented. The percentage per parameter is defined as the ratio of the number of subjects with at least one PCS value occurring at a post baseline visit that is more extreme than their baseline value and the total number of subjects in the subject sample with a post baseline measurement of the specified parameter.

In addition, all vital signs data will be presented as follows:

- VSL001 A listing of PCS values together with standard demographic data will be presented by-subject and within-subject by PCS vital signs test criterion by visit.
- VSL002 Vital signs data will be presented by-subject and within-subject by vital signs test and visit.

Study Specific Presentations

- VST003 For each variable with a PCS criterion (as presented in [Table 5](#)), the incidence of PCS values will be presented by visit. For a specific visit, the percentage per parameter is defined as the ratio of the number of subjects with at least one PCS value occurring at a specific post-baseline visit that is more extreme than their baseline value and the total number of subjects in the subject sample with a post baseline measurement of the specified parameter for the visit.

9.11.4 Electrocardiogram (ECG) Evaluations

Subject Samples:	Tables	Not applicable
	Listings	All subjects consented
	Figures	Not applicable
Subgroups:		Not applicable
Abbreviation:		EG

Standard Presentations

Standard ECG parameters and any abnormal findings, if applicable, will be presented in subject data listings as follows:

- EGL001 ECG data will be presented by-subject and within-subject by visit and parameter and/or findings.

EGL002 ECG data will be presented by-subject and within-subject by parameter. PCS values will be identified and only subjects with one or more PCS values for the parameter will be presented.

9.11.5 Other Safety Analyses

Other safety analyses will include device complications, PEG and J tube replacements and average duration, the sleep attack questions, Minnesota Impulsive Disorder Interview (MIDI), Columbia Suicide Severity Rating Scale (C-SSRS), melanoma check and neurological examination. Device complications will be reported on a per-subject basis. This implies that even if a subject reported the same complication repeatedly (complications that map to the same PT or that result in the same action taken), the complication will be counted only once.

Subject Samples:	Tables	Safety sample and US subset of safety sample
	Listings	All subjects consented
	Figures	Not applicable
Subgroups:		Not applicable
Abbreviation:		DC, DI, PE, QS

Study Specific Presentations

- DCT001 The incidence of device complications overall and by complication type will be presented, for all centers/countries combined, using default summary statistics. A table will be produced for all device complications as well as for the subset of device complications that resulted in an AE.
- DCT002 The incidence of device complications overall and for each MedDRA PT will be presented, for all centers/countries combined, using default summary statistics. A table will be produced for all device complications as well as for the subset of device complications that resulted in an AE.

- DCT003 The incidence of device complications overall and for each MedDRA PT will be summarized within each 3005 Treatment Year (as defined in Section 6.4.9), for all centers/countries combined, using default summary statistics. A table will be produced for all device complications as well as for the subset of device complications that resulted in an AE.
- DCT004 The incidence of device complications overall and for each action taken will be presented, for all centers/countries combined, using default summary statistics. A table will be produced for all device complications as well as for the subset of device complications that resulted in an AE.
- DCT005 Overview of Device Complications including the number of subjects with:
- At least one device complication
 - At least one device complication with action taken of tube replacement (either with or without surgery)
 - At least one device complication with an associated adverse event
 - At least one device complication with an associated adverse event and action taken of tube replacement (either with or without surgery).
- DCT006 Overview of Device Complications (same categories as DCT005) for each 3005 Treatment Year (as defined in Section 6.4.9).
- DIT001 A summary of PEG tube replacements will be presented, for all centers/countries combined, using default summary statistics. A similar summary will be presented for J tube replacements.
- DIT002 A summary of PEG tube and J tube replacements will be presented for each 3005 Treatment Year (as defined in Section 6.4.9).
- DIT003 The average PEG tube and J tube duration in Study 3005 will be summarized with default summary statistics and with the number and percentage of subjects with average durations in 3 month time intervals (≤ 91 days, 92 – 182 days, 183 to 273 days, 274 to 365 days, or > 365 days).
- QST001 A summary of sleep attacks will be presented, for all centers/countries combined, using default summary statistics.

- QST002 A summary of the development of intense impulsive behavior as assessed by the Minnesota Impulsive Disorders Interview (MIDI) will be presented, for all centers/countries combined, using default summary statistics.
- QST003 A summary of suicidal ideation and behavior as assessed by the Columbia Suicide Severity Rating Scale (C-SSRS) will be presented, for all centers/countries combined, using default summary statistics.

In addition, the other safety analysis data will be presented as follows:

- DCL001 A listing of device complications with the standard demographic data will be presented by-subject.
- DIL001 A listing of device information with the standard demographic data will be presented by-subject.
- PEL001 A listing of results of melanoma checks with the standard demographic data will be presented by-subject and within-subject by visit.
- QSL008 A listing of sleep attack responses with the standard demographic data will be presented by-subject and within-subject by visit.
- QSL009 A listing of MIDI responses and positive/negative assessment for impulsive behavior with the standard demographic data will be presented by-subject and within-subject by visit.
- QSL010 A listing of C-SSRS responses with the standard demographic data will be presented by-subject and within-subject by visit.

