8.5.5.1 Complications with Infusion Device

For each complication related to the infusion device (i.e., tubing kinks, tubing displaced, tubing connector problems, and pump technical difficulties) the following data will be collected in addition to a description of the complication.

- Incident start and stop date
- Type of complication
 - Pump complication

- Intestinal tube complication
- PEG-J complication
- Stoma complication
- Other complication
- Action taken
 - No action taken
 - Reposition of tube with surgery
 - Reposition of tube without surgery
 - Pump replaced
 - Medication treatment interrupted
 - Medication treatment stopped
 - Other
- Did this complication result in an AE? ("Yes" or "No")
- For complications that resulted in an AE, the AE number(s)

Each device complication will be assigned to a Preferred Term (PT), according to the MedDRA thesaurus, Version 14.0.

The percentage of subjects with a device complication will be determined as the number of subjects with at least one device complication relative to the number of subjects at risk. A subject will be considered at risk if the subject is in the Safety subject sample. Summaries of device complications by action taken will exclude complications where the response for action taken is "No action taken."

The incidence of device complications during each 3005 Treatment Year will be summarized using the study day intervals described in Section 6.4.9. Device complication start days and Treatment Period end days will be calculated relative to the start of 3005 LCIG infusion (RFSTDTN) as follows:

$$\text{Device Complication Start Day} = (\text{Device Complication Start Date} - \text{Date of First 3005 LCIG Infusion}) + 1$$

$$\text{Treatment Period End Day} = ([\text{Date of Last 3005 PEG-J Exposure} + 30 \text{ Days}] - \text{First Date of 3005 LCIG Infusion}) + 1$$

The count (and numerator for percentage calculations) will be the number of subjects who had their first occurrence of the PT start within the study day range for the 3005 Treatment Year. Each subject will be counted at most once within each SOC and PT.

The denominator for percentage calculations will include all subjects whose Treatment Period End Day is within or greater than the study day range for the 3005 Treatment Year.

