LBL002	14.3__4.4.3	Listing of Chemistry Determinations SAFETY SAMPLE – NARROW POLYNEUROPATHY SUBSET
VST001	14.3__5.1.1	Summary of Supine Systolic Blood Pressure (mmHg) SAFETY SAMPLE
VST001	14.3__5.1.2	Summary of Standing Systolic Blood Pressure (mmHg) SAFETY SAMPLE
VST001	14.3__5.1.3	Summary of Orthostatic Systolic Blood Pressure (mmHg) SAFETY SAMPLE
VST001	14.3__5.1.4	Summary of Supine Diastolic Blood Pressure (mmHg) SAFETY SAMPLE
VST001	14.3__5.1.5	Summary of Standing Diastolic Blood Pressure (mmHg) SAFETY SAMPLE
VST001	14.3__5.1.6	Summary of Orthostatic Diastolic Blood Pressure (mmHg) SAFETY SAMPLE
VST001	14.3__5.1.7	Summary of Supine Pulse (bpm) SAFETY SAMPLE
VST001	14.3__5.1.8	Summary of Standing Pulse (bpm) SAFETY SAMPLE
VST001	14.3__5.1.9	Summary of Orthostatic Pulse (bpm) SAFETY SAMPLE
VST001	14.3__5.1.10	Summary of Temperature (Celsius) SAFETY SAMPLE
VST001	14.3__5.1.11	Summary of Weight (kg) SAFETY SAMPLE
VST002	14.3__5.2.1	Number and Percent of Subjects with Potentially Clinically Significant Vital Sign Values SAFETY SAMPLE
VST003	14.3__5.2.2	Number and Percent of Subjects with Potentially Clinically Significant Vital Sign Values by Visit SAFETY SAMPLE
VSL001	14.3__5.2.3	Listing of Potentially Clinically Significant Vital Sign Parameters SAFETY SAMPLE
DCT005	14.3__6.1.1	Overview of Device Complications SAFETY SAMPLE
DCT006	14.3__6.1.2	Overview of Device Complications by 3005 Treatment Year SAFETY SAMPLE

SAP Table Code	Table Number	Table Title
DCT001	14.3__6.1.3	Number and Percent of Subjects with Device Complications by Type SAFETY SAMPLE
DCT002	14.3__6.1.4	Number and Percent of Subjects with Device Complications by MedDRA Preferred Term SAFETY SAMPLE
DCT003	14.3__6.1.5	Number and Percent of Subjects with Device Complications by MedDRA Preferred Term and 3005 Treatment Year SAFETY SAMPLE
DCT004	14.3__6.1.6	Number and Percent of Subjects with Device Complications by Action Taken SAFETY SAMPLE
DCT002	14.3__6.1.7	Number and Percent of Subjects with Device Complications with Action Taken of Tube Replacement by MedDRA Preferred Term SAFETY SAMPLE
DCT001	14.3__6.2.1	Number and Percent of Subjects with Device Complication Related to Adverse Events by Type SAFETY SAMPLE
DCT002	14.3__6.2.2	Number and Percent of Subjects with Device Complication Related to Adverse Events by MedDRA Preferred Term SAFETY SAMPLE

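### The device overview tables count tube replacement as an action taken, but the SAP's list of collected actions has only tube repositioning; the two must be reconciled against the CRF

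*SAP*

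**What the plan says.** For each complication of the infusion device, SAP 8.5.5.1 states that "the following data will be collected in addition to a description of the complication". It then gives the responses for action taken, which include "Reposition of tube with surgery" and "Reposition of tube without surgery". The remaining responses are no action, replacement of the pump, interruption of medication, stopping of medication, and other.

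SAP 9.11.5 specifies DCT005, an overview with four rows. One row is "At least one device complication with action taken of tube replacement (either with or without surgery"). Another is "At least one device complication with an associated adverse event and action taken of tube replacement (either with or without surgery"). DCT006 is specified as "Overview of Device Complications (same categories as DCT005) for each 3005 Treatment Year". SAP 12.2 adds Table 14.3__6.1.7, titled "Number and Percent of Subjects with Device Complications with Action Taken of Tube Replacement by MedDRA Preferred Term".

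Tube replacements have a separate source. Under SAP 8.5.5.2 they are derived from the PEG and J tube placement and removal dates on the Device Information eCRF, and DIT001 and DIT002 summarize them.

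**The concern.** The outputs select complications by a response that the SAP's own list of collected responses does not contain. A programmer would have to choose a mapping, and the SAP gives no rule for it. The closest match in the list is the pair of repositioning responses, because only they are divided by surgery.

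Repositioning and replacement are different events in these documents. Protocol 7.1 treats repositioning after displacement separately from the yearly assessment of whether the PEG-J needs replacing. Protocol 10.1.2 and 11.1.14 deal with replacement, and 10.6.1 and 11.1.12 with repositioning.

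Protocol 13.1 makes long-term safety the primary statistical objective, and 13.3 names the incidence of device complications among the safety analyses. A reader of the overview would take these rows as the number of subjects whose complication led to a new tube.

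**Working it through.** No arithmetic beyond counting applies, and the plan gives no figure to reproduce. The check sets the collected responses against the reported categories.

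**1. Collected responses (SAP 8.5.5.1).** There are seven:

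| Response | Concerns the tube? | Split by surgery? | Worded as replacement? |
|---|---|---|---|
| No action | no | no | no |
| Repositioning, with surgery | yes | yes | no |
| Repositioning, without surgery | yes | yes | no |
| Pump replacement | no | no | yes, of the pump |
| Medication interrupted | no | no | no |
| Medication stopped | no | no | no |
| Other | not stated | no | not stated |

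Responses that name tube replacement: 0 of 7. Responses that name the tube and are split by surgery: 2 of 7, both repositioning.

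**2. Reported categories.** Two of the four DCT005 rows use tube replacement, with or without surgery. DCT006 takes over the same categories, so the same two rows appear for each treatment year. Table 14.3__6.1.7 rests wholly on this selection. It is coded DCT002, but the DCT002 entry in 9.11.5 describes only all complications and those that resulted in an AE. For this table the tube-replacement subset is therefore named only in the title.

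**3. Possible sources for the rows, if the list is accurate.**

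- *The two repositioning responses.* The surgery wording fits, but the label does not.
- *A literal match.* No response qualifies, so the rows have no coded source.
- *The response other, read with the free description.* A replacement could be recorded there, but the SAP gives no rule for extracting it.
- *Device Information dates.* These identify replacements, but they are not an action-taken response and the SAP does not link them to complications.

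The first is the most natural choice. None of the four can be produced from the SAP as written with a correct label.

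**4. Consistency with other outputs.** DCT004 reports incidence for each action taken, leaving out the no-action response under 8.5.5.1. If the repositioning responses feed DCT005, the same records would be called repositioning in DCT004 and replacement in DCT005.

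**5. Explanation elsewhere.** SAP 10.1, which records changes to the planned analyses, does not address the label.

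**The case against.** The strongest reply is that the direction of the error is unknown. The CRF is not among the documents, and 8.5.5.1 is only the SAP's account of it. The outputs in 9.11.5 and 12.2 use the replacement wording consistently, whereas the repositioning responses appear in a single list. The SAP also has other slips between sections. EGL002 is a listing of potentially clinically significant values in 9.11.4 but a central-reader listing in 12.3, although 8.5.4 has ECGs read locally. SCL001 stands for two different listings in 12.3. If the list is the faulty text, relabelling the tables would put a wrong name on correct counts. This stands, and it is why the CRF must be checked first.

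Three stronger readings are tempting, and the documents do not support them:

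- *That the CRF has no tube-replacement option.* The documents show only the SAP's list.
- *That repositionings will certainly be reported as replacements.* The surgery wording makes this likely, but the response other, with its description, leaves another route open.
- *That a difference from DIT001 and DIT002 would prove the error.* Those tables count all PEG and J tube replacements, including ones with no preceding complication. They should differ from DCT005 even if every label were right.

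It is also fair to say that DCT004 shows the collected responses separately and that DCL001 and DIL001 list complications and device information by subject. A careful reader could detect a mislabelled row, but these outputs do not correct it.

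**Conclusion.** The inconsistency is real: SAP 8.5.5.1 and SAP 9.11.5 with 12.2 cannot both be right as written. The further conclusion, that the rows lack a coded source as labelled and would most likely show repositionings under the name of replacements, holds on the assumption that 8.5.5.1 reproduces the CRF. If the CRF does offer replacement, the fault lies in 8.5.5.1 instead, and that list needs correcting.

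The reach is two of four rows in DCT005, the same two rows in DCT006, and all of Table 14.3__6.1.7. How far the counts would mislead depends on how often tubes were repositioned rather than replaced after a complication, and the documents give no figure for this. The tables are descriptive, so no test, sample size or error rate is affected. This goes beyond a spelling slip, because the label decides which events a safety overview claims to count.

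**What to change.** Compare SAP 8.5.5.1 with the device complication CRF and use one term throughout.

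- If the CRF collects repositioning, relabel the two rows in DCT005 and DCT006 and the title of Table 14.3__6.1.7 as tube repositioning (with or without surgery). Leave replacements to DIT001 and DIT002.
- If the CRF collects replacement, correct the list in 8.5.5.1 and keep the table labels.

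In either case, state in 9.11.5 which response codes feed these rows, and describe the subset used for Table 14.3__6.1.7. The cost is one check against the CRF and text changes in the SAP and table shells; no new data are needed.

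A row for complications followed by a replacement, derived from Device Information placement dates, is optional. It would be a new derivation with its own rules: a stated linkage window, restriction to tube-related complications, and handling of missing stop dates. Linking on the complication's start and stop dates alone would not do, because it would attribute a routine tube change during a long complication to that complication and miss a replacement made after the recorded stop date.

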10.0 Changes to Planned Analyses

10.1 Changes to the Analysis as Laid Down in the Protocol and Amendments

The protocol statistical methods (Section 6.2 and Section 13.3) stated that for the analysis of change from baseline in efficacy measures, each subject's baseline will be their baseline measure in the first LCIG study in which they participated (e.g., Studies S187.3.001, S187.3.002 or S187.3.004). To focus the analysis on the maintenance of efficacy during participation in Study 3005, each subject's baseline value for the analysis of change from

baseline in efficacy measures will be the final value in the preceding open-label study. To provide context, the change in each efficacy measure from initial LCIG infusion to 3005 endpoint will also be determined and summarized.

Protocol Section 12.1.4 identifies the following as adverse events of special interest:

- Risks of PEG-J insertion
- Long-term complications of PEG-J
- Device-associated gastrointestinal disorders during long-term therapy

For consistency with current practice throughout the LCIG development program, these 3 categories have been combined into a single category of procedure and device associated events (Duodopa product specific CMQ).

12.0 Appendices

12.1 Schedules of Assessments

12.1.1 Schedule of Assessments – Amendment 1

Visit	Baseline	Six Monthly Visit	Termination	Follow-up*
Day	Termination Visit of Previous Study (003/004)	+/- 14 Days	-----	Termination Visit + 7 Days
Informed consent	X			
Inclusion/ exclusion	X			
Physical exam	X ^A	X	X	
Weight	X ^A	X	X	
Vital signs	X ^A	X	X	X
12-lead ECG ^B	X ^A	X ^B	X	
Clinical labs ^B	X ^A	X ^B	X	
β-HCG ^C	X ^A	X	X	
Adverse events	X ^A	X	X	X
Concomitant medication	X ^A	X	X	
Sleep attacks	X ^A	X	X	
Melanoma check	X ^A	X ^D	X	
Determination of continued benefit**	X	X		
MIDI	X ^A	X	X	
Complications with infusion device	X ^A	X	X	
Inspection of stoma	X ^A	X	X	X
Assessment of the need to replace PEG-J***	X	X ^D		
Dispensing of study drug	X	Every 6 weeks ^E		

^A Termination visit assessment from the previous trial will serve as the Baseline Assessment for this item.

^B Will be done as clinically indicated

^C For women of childbearing potential

^D Assessment performed once yearly

^E Clinical supply visits should take place every 6 weeks ± 1 week.

These visits will take at the hospital pharmacy and are for the sole purpose of dispensing clinical study drug and ancillary supplies.

* This visit needs to be performed only if PEG-J is removed, or if the subject does not continue to receive drug after termination.

**The decision to continue subjects on LCIG treatment will be dependent upon Principle Investigator's clinical judgment.

***On a yearly basis the LCIG system check needs to be evaluated by the study gastroenterologist; frequency of replacement should be in accordance with local practice.

12.1.2 Schedule of Assessments – Amendment 2

Visit	Baseline	6 Monthly Visit	Termination	Follow-up ⁺
Day	Final Assessment in Previous Study	+/- 14 Days	--	Termination Visit + 7 Days
Informed consent	X			
Inclusion/exclusion	X			
Physical exam	X ^a	X	X	
Neurological Exam	X ^a	X	X	
Weight	X ^a	X	X	
Vital signs	X ^a	X	X	X
12-lead ECG	X ^a	X ^b	X	
Clinical labs	X ^a	X ^b	X	
Folic Acid, Vitamins B6, B12, Methylmalonic Acid (MMA), and Homocysteine Levels	X ^a	X	X	
β-HCG ^c	X ^a	X	X	
Adverse events	X ^a	X	X	X
Concomitant medication	X ^a	X	X	X
Sleep attacks	X ^a	X	X	
Melanoma check	X ^a	X ^d	X	
Determination of continued benefit ^{**}	X	X		
MIDI	X ^a	X	X	
Complications with infusion device	X ^a	X	X	
Inspection of stoma	X ^a	X	X	X
Assessment of the need to replace PEG-J ^{***}	X	X ^d		
Dispensing of study drug	X	Every 6 weeks ^o		
Removal of PEG ^{****}			X	

* This visit needs to be performed only if PEG-J is removed, or if the subject does not continue to receive drug after termination.

** The decision to continue subjects on LCIG treatment will be dependent upon Principal Investigator's clinical judgment.

*** On a yearly basis, the LCIG system check needs to be evaluated by the study gastroenterologist; frequency of replacement should be in accordance with local practice.

**** For subjects deemed inappropriate for continued treatment by the Investigator, or for subjects who elect not to continue LCIG treatment, the PEG-J will be removed, and a follow-up clinic visit will occur 1 week later.

- The final assessment in the previous open-label LCIG study will serve as the baseline assessment for this item.
- Will be done as clinically indicated.
- For women of childbearing potential.
- Assessment performed once yearly.
- Clinical supply visits should take place every 6 weeks ± 7 days. These visits will take place at the hospital pharmacy and are for the sole purpose of dispensing clinical study drug and ancillary supplies.

12.1.3 Schedule of Assessments – Amendment 3

Visit	Baseline	6 Monthly Visit	Termination	Follow-Up*
Day	Final Assessment in Previous Study	+/- 14 Days	--	Termination Visit + 7 Days
Informed consent	X			
Inclusion/exclusion	X			
Physical exam	X ^a	X	X	
Neurological Exam	X ^a	X	X	
Weight	X ^a	X	X	
Vital signs	X ^a	X	X	X
12-lead ECG	X ^a	X ^b	X	
Clinical labs	X ^a	X ^b	X	
Folic Acid, Vitamins B ₆ , B ₁₂ , Methylmalonic Acid (MMA), and Homocysteine Levels	X ^a	X	X	
β-HCG ^c	X ^a	X	X	
Adverse events	X ^a	X	X	X
Concomitant medication	X ^a	X	X	X
Sleep attacks	X ^a	X	X	
Melanoma check	X ^a	X ^d	X	
Determination of continued benefit**	X	X		
MIDI	X ^a	X	X	
C-SSRS ^f	X ^a	X	X	X
Complications with infusion device	X ^a	X	X	
Inspection of stoma	X ^a	X	X	X
Assessment of the need to replace PEG-J***	X	X ^d		
Dispensing of study drug	X	Every 6 weeks ^e		
Removal of PEG****			X	

* This visit needs to be performed only if PEG-J is removed, or if the subject does not continue to receive drug after termination.

- ** The decision to continue subjects on LCIG treatment will be dependent upon Principal Investigator's clinical judgment.
- *** On a yearly basis, the LCIG system check needs to be evaluated by the study gastroenterologist; frequency of replacement should be in accordance with local practice.
- ****For subjects deemed inappropriate for continued treatment by the Investigator, or for subjects who elect not to continue LCIG treatment, the PEG-J will be removed, and a follow-up clinic visit will occur 1 week later.
 - a. The final assessment in the previous open-label LCIG study will serve as the baseline assessment for this item.
 - b. Will be done as clinically indicated.
 - c. For women of childbearing potential.
 - d. Assessment performed once yearly.
 - e. Clinical supply visits should take place every 6 weeks \pm 7 days. These visits will take place at the hospital pharmacy and are for the sole purpose of dispensing clinical study drug and ancillary supplies. When scheduling the 6 weekly drug dispensing visits, the site should always refer back to the baseline visit. Every attempt should be made to bring the subject back on the original targeted dates (\pm 7 days).
 - f. The "Already Enrolled Subjects" C-SSRS is to be the first assessment scale administered to the subject. At each subsequent assessment, the "Since Last Visit" C-SSRS scale should be administered. If the subject has previously completed the "Already Enrolled Subjects" scale in Study S187.3.003, the subject should complete the "Since Last Visit" scale at all scheduled time points outlined in Table 2 in this study. For subjects with a C-SSRS completed at their Study S187.3.003 final visit, that Study S187.3.003 final visit C-SSRS assessment will be considered baseline for Study S187.3.005. For all other subjects, the first C-SSRS assessment completed in this study will serve as baseline.

12.1.4 Schedule of Assessments – Amendment 4

Visit	Baseline	6 Monthly Visit	Termination/ Transfer to Commercial	Follow-Up*
Day	Final Assessment in Previous Study	+/- 14 Days	--	Termination Visit + 7 Days
Informed consent	X			
Inclusion/exclusion	X			
Physical exam	X ^a	X	X	
Neurological Exam	X ^a	X	X	
Weight	X ^a	X	X	
Vital signs	X ^a	X	X	X
12-lead ECG	X ^a	X ^b	X	
Clinical labs	X ^a	X ^b	X	
Folic Acid, Vitamins B ₆ , B ₁₂ , Methylmalonic Acid (MMA), and Homocysteine Levels	X ^a	X	X	
β-HCG ^c	X ^a	X	X	
Adverse events**	X ^a -----X			
Concomitant medication	X ^a	X	X	X
Sleep attacks	X ^a	X	X	
Melanoma check	X ^a	X ^d	X	
Determination of continued benefit***	X	X		
MIDI	X ^a	X	X	
C-SSRS ^f	X ^a	X	X	X
Complications with infusion device	X ^a	X	X	
Inspection of stoma	X ^a	X	X	X
Assessment of the need to replace PEG-J****	X	X ^d		
Dispensing of study drug	X-----Every 6 weeks ^e -----			
Daily Dosing Diary ^g		X	X	
Parkinson's Disease Diary ^g		X	X	
UPDRS ^h		X	X	
PDQ-39 ^h		X	X	
Removal of PEG*****			X	

- * This visit needs to be performed only if PEG-J is removed, or if the subject does not continue to receive drug after termination.
- ** Collection of adverse events is an ongoing and continuous process, not only occurring during site visits.
- *** The decision to continue subjects on LCIG treatment will be dependent upon Principal Investigator's clinical judgment.
- **** On a yearly basis, the LCIG system check needs to be evaluated by the study gastroenterologist; frequency of replacement should be in accordance with local practice.
- ***** For subjects deemed inappropriate for continued treatment by the Investigator, or for subjects who elect not to continue LCIG treatment, the PEG-J will be removed, and a follow-up clinic visit will occur 1 week later.
 - a. The final assessment in the previous open-label LCIG study will serve as the baseline assessment for this item.
 - b. Will be done as clinically indicated.
 - c. For women of childbearing potential.
 - d. Assessment performed once yearly.
 - e. Clinical supply visits should take place every 6 weeks \pm 7 days. These visits may take place at the hospital pharmacy and are for the purpose of dispensing clinical study drug and ancillary supplies. Other assessments may be completed during these visits if required. When scheduling the 6 weekly drug dispensing visits, the site should always refer back to the baseline visit. Every attempt should be made to pick up drug on the original targeted dates (\pm 7 days).
 - f. The "Already Enrolled Subjects" C-SSRS is to be the first assessment scale administered to the subject. At each subsequent assessment, the "Since Last Visit" C-SSRS scale should be administered. If the subject has previously completed the "Already Enrolled Subjects" scale in Study S187.3.003, the subject should complete the "Since Last Visit" scale at all scheduled time points in this study. For subjects with a C-SSRS completed at their Study S187.3.003 final visit, that Study S187.3.003 final visit C-SSRS assessment will be considered baseline for the Study S187.3.005. For all other subjects, the first C-SSRS assessment completed in this study will serve as baseline.
 - g. The Daily Dosing Diary and the Parkinson's Disease Diary will be completed by subjects or their caregivers for the 3 consecutive days prior to each clinic visit at US sites only.
 - h. The UPDRS and the PDQ-39 will be completed at US sites only.

